Statistical Analyses. We will use intention-to-treat principles in full accordance with CONSORT guidelines. We will monitor serious adverse events regularly to maintain up-to-date safety information for reporting to the DSMB. All data will undergo range checks at the time of data entry and will be examined monthly by histograms and bivariate scatterplots to check for inconsistencies, unusual data needing further verification, and outliers. Plots of longitudinal observations will be used to inspect for unusual changes requiring verification against source documentation. Regression diagnostics and exploratory analyses will be performed to find appropriate transformations of variables if needed. Order of priority in choosing a transformation will be to satisfy: 1) linearity, 2) homogeneity, and 3) normality assumptions. We will attempt to identify baseline covariates that predict attrition and compliance; and if such covariates can be identified, the analyses may need to incorporate stratification by these factors to decrease bias. In addition, following the recommendations of the 2010 National Academy of Sciences report,¹¹⁰ if the outcome is found to be missing at random, we will attempt to identify baseline covariates that predict attrition and use these covariates to impute missing data based on multiple imputation. Sensitivity analyses, using methods like pattern mixture models, will be carried out to explore the effect of missing outcomes on inference (if found to be not at random). Additionally, we will conduct sensitivity analyses of efficacy taking into account treatment compliance as a binary (compliers defined as >80% of prescribed vest wear time, >80% resistance training attendance, >80% of weight loss target) or continuous variable (proportion of treatment received).

Sample Size and Power. A total sample size of 150 (n=50 per group) is optimal to test hypotheses for the primary study aims. Using co-primary hypotheses demands use of a conservative Bonferroni correction of dividing the Type I error rate (α) in half for each aim to determine statistical significance.

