Aim 1, Hypothesis 1. Based on our preliminary data demonstrating effectiveness of the WL+VEST intervention in preserving total hip abMD, as well as effect size estimates generated from an 18 month trial of WL versus WL+RT on total hip vBMD, we anticipate that the WL+VEST group will decrease 3% from a baseline total hip vBMD value of 0.300 g/cm³ over 12 months compared to 5.5-6.0% decrease in the WL alone group, leading to a difference range of 2.5-3.0%. In **Table 4**, we observe that assuming 12 month group differences in total hip vBMD between 0.0075 and 0.009 g/cm³, we have at least 85% power to detect a statistically significant difference for the primary outcome assuming common group standard deviations of 0.010 g/cm³ and using a 2-sided t-test under differing retention scenarios over 12 months at a

Table 4. Power for Aim 1, Hypothesis 1.

12 Month Δ Total Hip vBMD g/cm ³ : WL+VEST (Δ %)	12 Month Δ Total Hip vBMD g/cm ³ : WL (Δ %)	12 Month Attrition		
		15%	13%	10%
		Power (%)*		
-0.009 (-3.0%)	-0.0165 (-5.5%)	87.7	88.6	89.7
-0.009 (-3.0%)	-0.018 (-6.0%)	96.7	97.1	97.5

* Assumes n=50/group and unadjusted SD=0.010 g/cm³ and $\alpha=0.025$ under 2-sided alternative hypothesis.

0.025 level of significance. Although we do not have pilot data specifically assessing total hip trabecular vBMD (only total hip vBMD, which is an integral measure of the trabecular and cortical regions), the two are highly correlated, with prior studies showing enhanced responsivity of the trabecular region.^{111,112} Thus, using total hip vBMD for our power calculations ensures adequate power for total hip trabecular vBMD as the primary outcome measure.

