Aim 1, Hypothesis 2. We anticipate that the change in total hip trabecular vBMD among the WL+VEST will be noninferior to the change among WL+RT. The noninferiority margin for the difference in 12-month total hip vBMD changes is -4% of baseline or -0.012 g/cm³, as used previously.¹¹³ Assuming 12-month equivalence between WL+VEST and WL+RT (i.e., WL+VEST and WL+RT 12 month mean are each 0.291 g/cm³), then a baseline sample size of 50/group provides >95% power to establish noninferiority of WL+VEST compared to WL+RT. This assumes 1) the same SD of change (0.010 g/cm³) as in Hypothesis 1; 2) attrition rate is a conservative 15% (better retention provides higher power); and 3) the Type I error rate is 0.0125, based on the convention of using 0.025 for a one-sided test, which is further divided in half due to having co-primary hypotheses.¹¹⁴ Alternately, using a smaller noninferiority bound provides a stricter standard for the trial objectives. Using a margin of -2.5% of baseline (-0.0075 g/cm³) difference between WL+VEST vs WL+RT, we have 85% power to establish noninferiority assuming the same SD as above (0.010 g/cm³), 15% attrition, and a 0.0125 Type I error rate.

Aim 2, Hypothesis 1. We note that the CT estimates were partially derived from DXA-measured aBMD loss under WL, which results in similar estimated BMD losses assumed between the two groups. We anticipate that the WL+VEST group will decrease 3% from a baseline total hip aBMD value of 1.027 g/cm² over 12 months compared to 5.5% decrease in the WL alone group, leading to a difference of 0.0257 g/cm², or 2.5% of baseline. Using this magnitude of difference, 50 participants/group will provide 90% power to detect a statistically significant difference for the primary outcome assuming common group standard deviation of change of 0.033 g/cm², based on a 2-sided t-test under 85% retention at 12 months using a 0.025 Type I Error rate.

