established at $p<0.025$. Next, the noninferiority of WL+VEST compared to WL+RT will be determined based on whether the lower bound of the one-sided confidence interval for the estimated 12 month treatment effect of WL+VEST versus WL+RT overlaps the -4.0% non-inferiority boundary for total hip trabecular vBMD. This will be performed using $\alpha=0.0125$ to account for co-primary hypotheses as well as for using a 1-sided alternative hypothesis. Tests for both co-primary hypotheses will be based on different contrast statements from the same statistical model. Secondarily, we will repeat these analyses with the short-term effect at 6 months of both interventions as an exploratory analysis. For Aim 2, we will repeat these analyses for the 12 month effect (and secondarily 6 month effect) using total hip aBMD assessed by DXA as the outcome. Comparisons will be performed for both superiority of WL+VEST vs. WL as well as noninferiority of WL+VEST vs WL+RT based on a 2.13% noninferiority margin using the methods described above. Analytic models for all other Aim 2 outcomes will mirror the model used in the primary aim, with the important exception that comparisons will focus on statistical comparisons of group mean differences. All outcomes are assessed at 6 and 12 months, and while both visit time points will be estimated, the 12 month treatment effect will be considered of primary interest. Treatment effects for changes in outcome variables are compared using a mixed model fit with treatment group, visit, and treatment by visit interaction, adjusted for sex and baseline values of the outcome. Tests will be performed using contrast statements at 12 months (primarily) and 6 months (secondarily), and we will use the partial F-test $p<0.05$ for significance. Significant comparisons for secondary outcomes will further use comparisons of all three groups at each visit using $p<0.0167$ for pairwise significance. Lastly, we intend to explore the associations between 6 and 12 month change in vBMD or aBMD with change in secondary outcome measures (i.e., DXA and CT-acquired body composition, D3Cr muscle mass, biomarkers of bone turnover, bone regulating hormones/cytokines) using linear regression methods and adjusted for sex and treatment group, to explore potential mechanisms underlying the treatment effect. Secondary comparisons will not be adjusted for multiplicity other than for pairwise group comparisons. Statistical analyses will be conducted using SAS v9.4 (SAS Institute, Cary, NC) and R software.

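### On the plan's own planning figures the -4% non-inferiority margin is 133-160% of the benefit implied for resistance training, and the non-inferiority conclusion is not tied to superiority over weight loss alone

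*Combined protocol and SAP*

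**What the plan says.** Sample Size and Power, Aim 1, Hypothesis 2, sets the margin: "The noninferiority margin for the difference in 12-month total hip vBMD changes is -4% of baseline or -0.012 g/cm³". Its support is a statement that the margin has been used before, with one citation. The same paragraph notes that a tighter bound of -2.5% of baseline (-0.0075 g/cm³) would be a stricter standard and gives 85% power for it. The Statistical Analysis Plan does not adopt that bound. Its decision rule asks whether the one-sided confidence bound "overlaps the -4.0% non-inferiority boundary for total hip trabecular vBMD".

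The expected losses are in the same section. Under Hypothesis 1, the vest group is expected to lose 3% from a baseline of 0.300 g/cm³, "compared to 5.5-6.0% decrease in the WL alone group, leading to a difference range of 2.5-3.0" per cent. Under Hypothesis 2, "WL+VEST and WL+RT 12 month mean are each 0.291" g/cm³, which is again a 3% loss.

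The two hypotheses are handled separately. Hypothesis 2 stands on its own under Objectives. On alpha, the plan says: "Using co-primary hypotheses demands use of a conservative Bonferroni correction of dividing the Type I error rate". On the tests, it says: "Tests for both co-primary hypotheses will be based on different contrast statements from the same statistical model". The non-inferiority step is introduced as coming next, which gives an order but not a condition. For the primary outcome only two contrasts are specified: vest versus WL, and vest versus RT. The overall hypothesis under Methods and Measures, however, is a joint one: the vest should do better than WL and about as well as RT.

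**The concern.** A non-inferiority margin against an active comparator is normally smaller than the comparator's own benefit over the control. Otherwise a treatment that does nothing can satisfy it. Here the planning figures put the margin above RT's implied benefit, and no text makes the conclusion about RT depend on beating WL.

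A split result is therefore possible: not superior to WL, yet non-inferior to RT. Under the plan as written, the second half could be reported as a met co-primary hypothesis, although it would not show that the vest preserves any bone. The plan does not say how such a result would be interpreted.

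**Working it through.** **Inputs, all from Sample Size and Power.** Baseline 0.300 g/cm³; loss 3.0% with vest and with RT; loss 5.5-6.0% with WL; SD of change 0.010 g/cm³; 50 per group less 15% attrition = 42.5; one-sided alpha 0.0125; margin 0.012 g/cm³.

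**Reproducing the plan's power (two-sample noncentral t, df = 2 × 42.5 - 2 = 83).**
- Non-inferiority at margin 0.012, true difference 0: 99.9% (plan: above 95%).
- Non-inferiority at margin 0.0075: 87.8% (plan: 85%).
- Superiority at differences of 0.0075 and 0.009, two-sided 0.025: 87.8% and 96.7% (Table 4: 87.7 and 96.7).

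The stated power figures are not in dispute.

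**Margin against RT's implied benefit.**
- Benefit = WL loss - RT loss = 5.5 - 3.0 = 2.5%, or 6.0 - 3.0 = 3.0%; that is 0.0075 or 0.009 g/cm³.
- Ratio = 0.012/0.009 = 1.33 to 0.012/0.0075 = 1.60.
- At the boundary the vest would lose 3.0 + 4.0 = 7.0%, more than the 5.5-6.0% assumed for WL.

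**What passes.** SE = 0.010 × √(2/42.5) = 0.00217. With t(0.9875, 83) = 2.283, the bound clears -0.012 whenever the observed vest-minus-RT difference is better than -0.012 + 2.283 × 0.00217 = -0.0070 g/cm³, about -2.3% of baseline.

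**A vest with no effect (vest = WL).** The true vest-minus-RT difference is then -0.0075 or -0.009, inside the margin. Chance of declaring non-inferiority:

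| SD of change | RT benefit 2.5% | RT benefit 3.0% |
|---|---|---|
| 0.008 (assumed) | 62% | 30% |
| 0.010 (plan) | 42% | 19% |
| 0.012 (assumed) | 30% | 13% |

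At a true difference of exactly -0.012 the chance is 1.25%, so the test has its stated size.

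**Split result.** A three-arm simulation (42.5 per arm, pooled variance, SD 0.010) gives non-inferior to RT but not superior to WL about 41% / 18% of the time for a vest with no effect. Both tests are won only about 1% of the time.

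**If RT itself gives no benefit over WL and the vest equals both,** non-inferiority is true but uninformative, and it is declared 99.9% of the time.

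**Larger assumed benefit (SD 0.010).** For a vest with no effect, the chance falls to 6% if RT's benefit is 3.5% and to 1.25% if it is 4.0%.

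**Contrast within the plan.** For hip aBMD (Aim 2, Hypothesis 2) the margin is -2.13%, tied to fracture risk. That is 2.13/2.5 = 85% of the benefit expected there. With margin 0.022, true difference -0.0257 and SD 0.033 g/cm², a vest with no effect passes 0.3% of the time.

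**The case against.** **The numbers describe an endpoint that is not tested.** The decision is on trabecular vBMD. The plan concedes this gap, "Although we do not have pilot data specifically assessing total hip trabecular vBMD", and expects a larger response there, "with prior studies showing enhanced responsivity of the trabecular region". No trabecular baseline, SD or effect is given. This stands: the probabilities are illustrations. The margin would fall below RT's benefit, however, only if that benefit exceeded 4% of baseline, and nothing in the plan says that it does.

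**RT's benefit is inferred.** It follows from the equal-means assumption made for power; the documents give no RT-versus-WL estimate or interval. This stands as a limit.

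**Hypothesis 1 already tests a vest with no effect,** from the same model, and the plan commits to CONSORT. A failed superiority test would therefore sit beside any non-inferiority result. This limits the harm. It does not say what may be concluded from the second result when the first fails.

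**Separate claims are a legitimate design.** Alpha is paid for each hypothesis, and a hard gate would make Hypothesis 2 almost a copy of Hypothesis 1. This is a fair objection to removing the formal Hypothesis 2 result, and the fix below does not remove it.

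**Stronger readings that the documents do not support.** A reader might infer that 42% or 19% is a false-positive rate to set against 1.25%. It is not: those true differences lie inside the stated margin, so the declaration is correct for the hypothesis as written. A reader might also infer that -4% is unjustified. The cited source is outside the documents, so all that can be said is that the plan never compares the margin with its own expected benefit.

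**Conclusion.** The point holds as one about a wide margin and a weak claim. On the plan's integral-vBMD figures the margin is 133-160% of RT's implied benefit, and no text links the non-inferiority conclusion to superiority over WL, although the overall hypothesis is joint. Followed exactly, the rule can call a vest with no effect non-inferior to RT; on the plan's inputs that happens about 42% or 19% of the time.

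The ratio rests on the equal-means assumption and on integral data standing in for trabecular data. The probabilities rest also on the SD of change, and adjustment for baseline in the planned model could move them upward. The missing link between the two conclusions depends on none of these assumptions. It should be fixed, and wording is enough.

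**What to change.** **1. Statistical Analysis Plan, after the non-inferiority rule, add:** *The conclusion that WL+VEST preserves bone similarly to WL+RT will be drawn only if WL+VEST is also superior to WL at 12 months. If it is not, the non-inferiority result will be reported together with the failed superiority test and will not be interpreted as evidence that the vest preserves bone.*

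**2. Sample Size and Power, Aim 1, Hypothesis 2, add:** *On the planning figures this margin exceeds the expected benefit of WL+RT over WL (0.0075-0.009 g/cm³), so non-inferiority alone does not show that any of that benefit is kept.*

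Both tests, their alphas and the margin stay as planned, and no participants are added.

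**Cost (SD 0.010).** When the vest truly equals RT, the chance of the full conclusion is 88-97%, against 99.9% for non-inferiority alone (73-88% for the full conclusion at an assumed SD of 0.012). The larger cost falls on a vest that keeps half of RT's benefit. The full conclusion is then reached 30% of the time instead of 94% (RT benefit 2.5%), or 41% instead of 88% (3.0%). The formal Hypothesis 2 result is still reported in every case.

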The **main goal** of this study is to compare the effects of WL alone with WL plus weighted vest use or WL plus RT on indicators of bone health and subsequent fracture risk. This is a 12 month trial in 150 older (60-85 years) adults with obesity (BMI=30-40 kg/m² or BMI= 27.0-<30 kg/m² plus one risk factor) randomized to one of three interventions (n= 50/group): WL alone (**WL**; caloric restriction targeting 10% WL with adequate calcium, vitamin D, and protein); WL plus weighted vest use (**WL+VEST**; targeting 8 hours/day, weight replacement titrated up to 10% WL); or, WL plus structured RT (**WL+RT**; targeting 3 sessions/week). In Version 11.4.2022

accordance with recent international position statements on the clinical use of computed tomography (CT) of the hip in the management of osteoporosis,^{63,64} total hip trabecular volumetric BMD (vBMD) is the primary outcome. This outcome will be complemented by exploratory assessment of several fracture-related risk factors, including: (1) femoral neck and lumbar spine vBMD, cortical thickness, finite element modeling of bone strength, and regional fat and muscle volumes, measured by CT; (2) aBMD at the total hip, femoral neck, lumbar spine, and distal radius; trabecular bone score; and total body fat/lean masses, measured by dual energy x-ray absorptiometry (DXA); (3) muscle function and strength; (4) biomarkers of bone turnover; and (5) bone-regulating hormones/cytokines known to influence bone metabolism during WL. Therefore, our Specific Aims are to:

Aim 1: Determine the effects of WL+VEST compared to WL and WL+RT on 12 month change in total hip trabecular vBMD. Despite similar reductions in total body weight, **Hypothesis 1:** Participants in the WL+VEST group will show attenuated losses of total hip trabecular vBMD versus WL; and **Hypothesis 2:** Loss in total hip trabecular vBMD will be no greater in WL+VEST compared to WL+RT.

Aim 2: Explore the effects of WL+VEST compared to WL and WL+RT on the 12 month change in fracture-related risk factors. Despite similar reductions in total body weight, we **hypothesize** that WL+VEST and WL+RT will demonstrate improvements in fracture-related risk factors compared to WL.

Methods and Measures

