Aim 2, Hypothesis 2. We anticipate that the change in total hip aBMD among the WL+VEST will be noninferior to the change among WL+RT. The noninferiority margin (i.e. difference at which a clinically meaningful increase of nonvertebral fracture risk may occur¹¹⁵) for the difference in 12 month total hip aBMD changes is -2.13% of baseline or -0.022 g/cm². Assuming equivalence between WL+VEST and WL+RT (i.e., WL+VEST and WL+RT 12 month mean are each 3% reduced from baseline (0.996 g/cm²) as used in Hypothesis 1), then a baseline sample size of 50/group provides 80% power to establish noninferiority of WL+VEST compared to WL+RT such that the lower bound of the one-sided 0.9875 confidence bound of the group mean differences will be greater than a -0.022 g/cm² difference between WL+VEST minus WL+RT. This assumes 1) the same common group SD of change (0.033 g/cm²) as in Hypothesis 1; 2) attrition rate is 15%; and 3) the Type I error rate is 0.0125, based on the convention of using 0.025 for a one-sided confidence interval, which is further divided in half due to having co-primary hypotheses.

Aim 2, All other outcomes. Due to the challenges of prespecifying noninferiority boundaries for exploratory outcomes, all other analyses for the second aim will focus on the three group comparisons of WL, WL+VEST, and WL+RT. Based on the same baseline sample size of 50/group (n=150 overall), we will have 80% power to detect a relatively modest effect sizes (variance of means/within-group variance) of 0.116 under the attrition rate of 15% assumed above, assuming 2-tailed F-test and a 0.05 Type I error rate.

Statistical Analysis Plan. The primary aim for comparisons of total hip trabecular vBMD will be tested using a mixed model fit using the change in total hip trabecular vBMD at 12 months versus the treatment effect indicator for each of the three groups, adjusted for visit (6 or 12 months), visit by treatment interaction, sex (to account for randomization strata) and baseline value. A contrast statement will test change in total hip trabecular vBMD at 12 months in WL versus WL+VEST, and a statistically significant difference will be

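### Is the noninferiority limit for total hip trabecular vBMD tied to the baseline of a different variable?

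*Combined protocol and SAP*

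**What the plan says.** The Objectives state Hypothesis 2 for the trabecular compartment: "Loss in total hip trabecular vBMD will be no greater in WL+VEST compared to WL+RT".

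Under Sample Size and Power, Aim 1, Hypothesis 1, the planning losses are taken "from a baseline total hip vBMD value of 0.300" g/cm³. The same paragraph says what pilot data exist: "only total hip vBMD, which is an integral measure of the trabecular and cortical regions". It argues that the two measures are highly correlated and that integral values may therefore serve for the power calculation.

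Under Aim 1, Hypothesis 2, the margin appears in two forms: "The noninferiority margin for the difference in 12-month total hip vBMD changes is -4% of baseline or -0.012" g/cm³. The planning means there are on the same footing: "WL+VEST and WL+RT 12 month mean are each 0.291" g/cm³. A stricter alternative of −2.5%, or −0.0075 g/cm³, is also given.

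The Statistical Analysis Plan paragraph then describes "a mixed model fit using the change in total hip trabecular vBMD at 12 months", adjusted for visit, visit by treatment, sex and baseline value. The noninferiority decision depends on whether the lower one-sided confidence bound "overlaps the -4.0% non-inferiority boundary for total hip trabecular vBMD", at one-sided α = 0.0125. No g/cm³ figure is given there.

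**The concern.** The two forms of the margin are joined as if they were interchangeable, yet they agree only at a mean baseline of 0.300 g/cm³, and that value belongs to integral vBMD. The documents give no trabecular baseline. They also do not say whether the modelled change is in g/cm³ or in percent, or whether the reference is each participant's baseline, a pooled mean or the planning value.

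A contrast estimated in g/cm³ cannot be set against −4.0% without a conversion, and the only conversion printed for this margin is −0.012. If that were used and the trabecular baseline were below 0.300, the vest arm could be declared noninferior at a relative deficit larger than 4%. If the baseline were above 0.300, the test would be stricter than 4%. Because this limit decides a co-primary hypothesis, a loose definition deserves a check.

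**Working it through.** **Origin of the absolute figures** (inputs from Sample Size and Power, Aim 1, Hypotheses 1 and 2)

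- 0.012 / 0.300 = 4.0%
- 0.0075 / 0.300 = 2.5%
- 0.300 × (1 − 0.03) = 0.291

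All three rest on the integral planning baseline.

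**The plan's power.** Inputs: SD of change 0.010 g/cm³, true difference 0, one-sided α = 0.0125, 50 per arm with 15% attrition, so 50 × 0.85 = 42.5 per arm. The standard error of the contrast is 0.010 × √(2/42.5) = 0.00217 g/cm³. Non-central t power:

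| Margin (g/cm³) | Margin/SD | Power | Stated |
|---|---|---|---|
| 0.012 | 1.20 | 99.9% | >95% |
| 0.0075 | 0.75 | 87.8% | 85% |

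The first figure is confirmed; the second is stated slightly low.

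**How far the two forms could differ.** For a trabecular mean baseline B, the absolute figure equals 0.012/B in relative terms, and 4% equals 0.04 × B in absolute terms. The values of B below are assumed, except 0.300, which is the plan's integral value.

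| B (g/cm³) | 0.012 as % of B | 4% of B (g/cm³) |
|---|---|---|
| 0.35 | 3.4 | 0.014 |
| 0.30 | 4.0 | 0.012 |
| 0.25 | 4.8 | 0.010 |
| 0.20 | 6.0 | 0.008 |
| 0.15 | 8.0 | 0.006 |

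The middle column matters only if −0.012 is applied to trabecular vBMD, which the analysis rule does not ask for.

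**Absolute or percent change.** If every participant has the same absolute deficit, equal to 4% of the mean baseline, and baselines are lognormal with coefficient of variation CV, the mean percent change is −4% × (1 + CV²). At assumed CVs of 15, 25 and 35% this is −4.09, −4.25 and −4.49%. The shift is 0.09 to 0.49 percentage points, against a contrast standard error of 0.00217/0.300 = 0.72 points on the planning scale.

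**Which participants supply the mean baseline.** With an assumed between-person SD of 0.05 g/cm³:

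- Standard error of a margin taken from all 150: 0.04 × 0.05/√150 = 0.00016 g/cm³.
- SD of the difference between a two-arm and a three-arm reference: 0.04 × 0.05 × √(1/100 − 1/150) = 0.00012 g/cm³.

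Both are small beside 0.00217.

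**Power if 4% is taken of a lower trabecular baseline.** If the SD of change scales with baseline, margin/SD stays at 1.20 and power at 99.9%. If the SD stayed at 0.010, power with 42 per arm would be 99%, 91% and 68% at B = 0.25, 0.20 and 0.15, and at least 95% for B of about 0.215 or more. The documents give neither the trabecular baseline nor its SD, so this range does not show that power is inadequate.

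**The case for a change.** The best argument for a change comes from the plan's treatment of areal BMD. Under Aim 2, Hypothesis 2, the confidence bound is compared with an absolute limit of −0.022 g/cm². The analysis paragraph then calls the same margin 2.13% and refers back to the methods already described. An analyst copying that pattern might read −4.0% as −0.012 g/cm³. For areal BMD the two forms match, because 1.027 g/cm² is the baseline of the tested variable (0.0213 × 1.027 = 0.0219). For trabecular vBMD no such match is shown. The correlation argument in the power section supports using integral data for power, but it does not make the two mean levels equal. The Statistical Analyses section also allows a transformation after diagnostics, so the scale is not fully fixed.

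Part of this stands. The scale and the level of the reference baseline are unwritten, and the areal BMD text points towards absolute change, which does need a conversion. But the pattern to copy is a percentage of the tested variable's own baseline. Followed consistently, it leads to 4% of the trabecular baseline and not to −0.012. Nor must the conversion wait for outcomes: Table 3 places the baseline CT before randomisation, and the percentage and the variable are already fixed. The transformation clause is conditional and does not alter the stated boundary.

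**Conclusion.** No change follows. The rule that decides Hypothesis 2 names the right variable and a definite size, −4.0% of trabecular vBMD. The −0.012 g/cm³ figure is that percentage evaluated at the planning baseline, in a section that says its inputs are integral values. What is missing is a detail that analysts fill sensibly: take 4% of the mean baseline of the modelled outcome, or model percent change and use −4.0% directly. Either choice carries out the plan's own rule, and under the assumed CVs they differ by at most about half a percentage point.

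The larger discrepancies, up to −8.0%, need both an assumed trabecular baseline as low as 0.15 g/cm³ and a use of −0.012 that the analysis rule does not direct. The documents settle neither their size nor their direction. The stated power holds on its own inputs and is not shown to be wrong for the trabecular measure. This conclusion assumes that the baseline meant in the margin is that of the tested variable, which is the natural reading of the analysis paragraph. The source cited for the 4% margin was not available, so the choice of 4% itself is not judged here.

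### For the exploratory Aim 2 outcomes other than total hip aBMD, the pairwise threshold of 0.0167 is stricter than needed after a same-visit three-arm F-test, and the pairwise power is not stated

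*Combined protocol and SAP*

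**What the plan says.** The Aim 2 hypothesis in Objectives is pairwise: "WL+VEST and WL+RT will demonstrate improvements in fracture-related risk factors compared to WL".

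The power paragraph for the remaining Aim 2 outcomes (Sample Size and Power, 'Aim 2, All other outcomes') concerns the three-arm test: "we will have 80% power to detect a relatively modest effect sizes (variance of means/within-group variance) of 0.116", with 15% attrition and "assuming 2-tailed F-test and a 0.05 Type I error rate". It gives no power for any pair of arms.

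The Statistical Analysis Plan says "Analytic models for all other Aim 2 outcomes will mirror the model used in the primary aim", then sets a partial F-test at p<0.05. After that, "Significant comparisons for secondary outcomes will further use comparisons of all three groups at each visit", at p<0.0167 per pair, which is 0.05/3. On multiplicity it adds "Secondary comparisons will not be adjusted for multiplicity other than for pairwise group comparisons".

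The two co-primary tests and total hip aBMD have their own superiority and noninferiority rules and do not use this procedure.

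**The concern.** The outcomes under this rule include femoral neck and spine vBMD, finite element bone strength, muscle function and bone turnover markers. For each, the hypothesis concerns WL+VEST vs WL and WL+RT vs WL, so the pairwise step decides it. A significant F-test does not show which arms differ.

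With exactly three arms, an F-test gate followed by unadjusted pairwise tests (Fisher's protected LSD) already controls the pairwise familywise error. A Bonferroni threshold placed behind that gate gives up power without being needed for the 5% limit. The only power figure a reader sees is 80%. A non-significant WL+VEST vs WL result could therefore be taken as evidence of no vest effect in a study thought to have 80% power for that comparison.

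**Working it through.** **Inputs from the plan.** 50 per arm and 15% attrition, so 0.85 × 50 = 42.5 completers per arm (the protocol gives 128 in total); effect size 0.116 (variance of means over within-group variance); F-test at 0.05; pairs at 0.0167.

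**Inputs assumed here.** The plan gives no pattern of means for these outcomes. The main case is WL = 0 and WL+VEST = WL+RT = d, the equality the plan assumes for total hip vBMD and aBMD. The check is a one-way comparison of completers; the mixed model with 6-month data was not simulated.

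**Step 1: the plan's own figure.** With variance-of-means divisor k−1 = 2, the noncentrality is 42.5 × 2 × 0.116 = 9.86. With 2 and 3 × 42.5 − 3 = 124.5 df, the critical F is 3.07 and the power is 79.96%. The stated 80% reproduces. With divisor k the power would be 93.5%, so k−1 is what the plan used.

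**Step 2: the effect in SD units.** For means (0, d, d) the variance with divisor 2 is (4/9 + 1/9 + 1/9)d²/2 = d²/3. Setting d²/3 = 0.116 gives d = √0.348 = 0.590 SD.

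**Step 3: familywise error at one visit, gate at that visit.**
- All three means equal: any false pairwise claim first needs a false F-test, so the error is at most 5%.
- Exactly one pair equal: only one claim can be false, and testing it at 0.05 caps the error at 5%.
- All means different: no claim of a difference is false.

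Simulation agrees. With no true difference the error is 5.0% for gate plus 0.05 and 4.2% as written. With WL+VEST = WL+RT and both 0.59 SD from WL, it is 4.9% and 1.7%; with a large shift in the third arm, 5.0% and 1.7%.

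**Step 4: power.** Simulation with pooled-variance t-tests, 43/43/42 completers, findings counted in the direction of benefit. Each cell shows the stated rule, then gate plus 0.05.

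| Means (WL, WL+VEST, WL+RT), SD | F-test | WL+VEST vs WL | Both vs WL |
|---|---|---|---|
| 0, 0.59, 0.59 | 80% | 62.0% / 72.5% | 46% / 64% |
| 0, 0.49, 0.65 (same 0.116) | 80% | 44% / 59% | 39% / 57% |
| 0, 0.34, 0.68 (same 0.116) | 80% | 20% / 34% | 19% / 33% |
| 0, 0.75, 0.75 | 95% | 85% / 92% | 76% / 88% |

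With equal arms of 42 or 43, the first row's last column is 45.2% / 63.3% or 46.6% / 64.7%.

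If 0.116 is read as unadjusted, and baseline correlates 0.3 or 0.5 with change (an assumed range; SD multiplied by √(1−r²)), both contrasts at 0.59 SD are found in about 52% / 69% or 64% / 79%.

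**Step 5: where the loss comes from.** At 0.59 SD, pairs at 0.0167 with no gate give 62.2% for WL+VEST vs WL and 46% for both, practically the same as with the gate. The loss comes from the threshold.

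**Step 6: detectable difference as written.** Noncentral t at 0.0167 with 42.5 per arm gives 80% power for one contrast at 0.71 SD. For 0.59 SD it needs about 61 completers per arm.

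**Step 7: if the gate is at the other visit.** Suppose a significant 12-month F-test opened the 6-month pairs, with 12-month means of 0, 0.59, 0.59 SD, no 6-month difference and visit correlation 0 to 0.7 (assumed). The 6-month familywise error is then 9 to 10% with pairwise 0.05 and 3 to 4% with 0.0167. The gate protects only the visit at which it is applied.

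**The case against.** The strongest objection is the wording on visits. The plan says "Tests will be performed using contrast statements at 12 months (primarily) and 6 months (secondarily" and then sends significant outcomes to pairwise tests at each visit. If a significant 12-month F-test opens the pairs at both visits, 0.0167 does necessary work at 6 months (Step 7). This stands: 0.0167 is redundant only with a same-visit gate, so any change must fix the visit as well as the threshold.

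Bonferroni over three pairs is also a valid, conventional choice, and the limb loading sub-study likewise follows an overall test with Bonferroni. That is fair, but at a given visit every result found under gate plus 0.0167 is also found under gate plus 0.05, and the latter stays within 5%. The gain is therefore more than a matter of taste.

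The outcomes are exploratory, the stated rule errs on the safe side, and there is no adjustment across many outcomes, so some restraint is useful. This also stands, and it limits the weight of the point.

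A reader might infer that the 80% statement is wrong. It is not: the plan ties it to the F-test, and it reproduces. A reader might also infer that adding the gate to Bonferroni causes the loss. Step 5 shows that the gate costs almost nothing.

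**Conclusion.** The point holds in a limited form. With a same-visit F-test gate, testing pairs at 0.0167 is stricter than three arms require. At the plan's effect size, with equal benefits of 0.59 SD and 42 to 43 completers per arm, it lowers the chance of finding WL+VEST vs WL from about 73% to 62%, and of finding both contrasts from about 64% to 46%. The plan states no power for these comparisons.

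It would be tempting to conclude that a real benefit of this size would usually fail to support the Aim 2 hypothesis. The documents do not support that. The 46% requires equal WL+VEST and WL+RT effects and both contrasts won on the same outcome. The plan assumes equal effects only for total hip vBMD and aBMD, and defines no success rule per outcome. Under the assumed baseline correlations of 0.3 and 0.5 the figure rises above half; with evenly spaced means it falls to 19%.

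This is lost sensitivity in exploratory outcomes, with no inflation of error. The change is worthwhile and cheap, but optional.

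**What to change.** In the Statistical Analysis Plan, replace the pairwise rule with: 'If the partial F-test at a visit is p<0.05, the three pairwise contrasts at that same visit are each tested at p<0.05; estimates and 95% CIs are reported for all three.'

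In 'Aim 2, All other outcomes', add the pairwise power with its assumed pattern: 'With 15% attrition and equal benefits of WL+VEST and WL+RT over WL, power to find both contrasts is about 64% at 0.59 SD and about 80% at 0.69 SD.' (Simulated at 0.69 SD: 80.7%.)

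If the sponsor prefers 0.0167, the F-test gate can be dropped at almost no change in power or error, and 0.71 SD should be given as the difference detectable with 80% power for one contrast. If a 12-month F-test is meant to open the 6-month pairs, 0.0167 should stay for those pairs.

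The change needs no new data, visits or model. Its price is more false positives within the 5% limit for each outcome and visit: 5.0% instead of 4.2% when no arms differ, and up to 5.0% instead of 1.7% for a single equal pair. With no adjustment across outcomes, false positives across the Aim 2 set would also rise, so these results should stay labelled exploratory.
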